6.1.3 Sample size

This is an observational study with non interventional design. Sample size calculation is made on the basis of previous data indicating that at least 2% absolute difference in Flow mediated dilatation (FMD) (corresponding to 20-30% relative difference) is considered significant and clinically relevant. With the null hypothesis being that CFZ/Dex therapy is associated with <10% relative difference in FMD and the alternative hypothesis being that a \geq 30% difference is considered as significant, and with an a=0.05, a sample of 40 patients is required for 90% power of detecting these differences (all tests are 2-sided). A dropout rate of 15% is assumed. A total number of 46 patients is thus calculated to be enrolled.

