Endothelial function will be assessed by Flow Mediated Dilatation (FMD) using a 7-14 MHz probe (Vivid 7 Pro, GE, USA) as previously described (27). After a 15-min rest in supine position in a quiet, climate-controlled room (22 ±1°C), the internal diameter of the brachial artery of the subject is assessed. Upper arm occlusion by supra-systolic level (50 mmHg above systolic blood pressure) is applied via a cuff fitted 8-cm distal to the brachial artery (in the antecubital fossa) and near the wrist for 5 min. The cuff is released following the 5-min inclusion to induce reactive hyperemia. This increase in shear stress results in endotheliumdependent flow-mediated dilation (FMD). Data are recorded 2 minutes before and immediately after cuff release to measure peak blood flow and brachial artery diameter for 2 min after cuff deflation. ECG-gated frames of brachial artery diameter are continuously recorded and brachial artery diameter is measured offline using dedicated border detection software (Brachial Analyzer for Research, MIA IIc, USA). Flow-mediated dilatation is induced in response to reactive hyperemia and is expressed as the percentage change of internal diameter of the brachial artery from baseline. Flow-mediated dilatation has been previously shown to be nitric oxide dependent in humans and it is considered as a marker of endothelial function (28-29). Ultrasound analysis will be performed in each case manually by a qualified independent observer blinded to the clinical history of the subjects.

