6.5 Measurement of circulating cardiac and vascular inflammatory biomarkers

Plasma and serum samples will be obtained by venipuncture on admission and stored at - 70°C. Plasma probes will be centrifuged for 15 minutes at 10.000 g within 30 minutes of

collection. Probes will be aliquoted and stored at -70°C till analysis. The concentrations of Creactive protein, interleukin 6, vascular cell and intercellular adhesion molecule-1, E-selectin, and monocyte chemoattractant protein-1 will be measured in ethylenediaminetetraacetic acid (EDTA)-plasma at the Oncology Laboratory of the Department of Clinical Therapeutics wellcharacterized enzyme immunoassays. N-terminal pro-B-type natriuretic peptide will be measured with a sandwich immunoassay on an Elecsys 2010 instrument (Roche Diagnostics). Serum cardiac troponin T concentrations will be measured using statndard procedures.

7. Timelines of the study

Vascular measurements and blood collection will be performed at baseline before and 2 hours after dexamethasone and carfilzomib administration. These measurements will be repeated as shown below:

	Before Dexa	After Dexa	Before & after CarD	After CarD	Before & after CarD								
Time points	d -2		d0	d2	d8	d9	d15	d16	C2d1	d2	C3d1	d2	C6d1or 6 months after baseline
Vascular studies	x	X	X†	X	Xt	X	Xt	X	Xt	X	Xt	x	t x
24h ambuatory BF monitoring	×		X*		Х*				X*		X*		X*
Cardiac US	X					1				. 8			X**
Blood for Proteasome activity			x	x	x	x	X?	x	x	x			Xt
Serum collection for cardiac biomarkers	×		×t		×t		×t		×t		x		x

Schedule of assessments

* During 24th of CarD

**Only before C6d1

†2 measurements/ samples at this day

The subjects will be evaluated for AE at all visits.

8. Data presentation and statistical analysis

Data will be presented as mean ± standard deviation (SD). Continuous variables will be tested for normal distribution with the Kolmogorov-Smirnov test. Repeated measures ANOVA will be performed in order to assess significant variations of parameters of interest over time. Linear mixed models analysis will be performed in order to adjust for possible confounders over time. All tests will be two-tailed and statistical significance will be considered for P

values less than 0.05. All statistical analyses will be performed using SPSS version 21 for windows (Chicago, ILL, USA).

9. Safety reporting

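### The inputs in section 6.1.3 cannot fix a sample size for a mean change in FMD, because no SD of the change is given; the stated 90% power is therefore unsupported

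*Protocol*

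**What the plan says.** Section 6.1.3 takes as relevant "at least 2% absolute difference in Flow mediated dilatation (FMD) (corresponding to 20-30% relative difference"). The hypothesis to be rejected is worded as "the null hypothesis being that CFZ/Dex therapy is associated with <10% relative difference in FMD". Its counterpart, on the same relative scale, reads "the alternative hypothesis being that a \geq 30% difference is considered as significant". From these, at the 5% level, the section concludes that "a sample of 40 patients is required for 90% power of detecting these differences (all tests are 2-sided"). It names no test and gives no SD, within-patient correlation or baseline FMD.

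Section 6.2.2 defines FMD as a continuous quantity: it "is expressed as the percentage change of internal diameter of the brachial artery from baseline". Section 8 gives the analysis: "Repeated measures ANOVA will be performed in order to assess significant variations of parameters of interest over time", with linear mixed models to adjust for confounders. The protocol defines no FMD responder and no proportion-of-patients endpoint for FMD.

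**The concern.** The power of a test of a mean within-patient change depends on the ratio of the change to its SD. Section 6.1.3 supplies the change but not the SD, yet presents 40 patients and 90% power as following from what it lists. For a proportion the position is different: the variance p(1−p) is fixed by p itself, so two percentages, an alpha and a power are enough to give an n. The listed inputs have exactly that form, and they give 40. But the section words 10% and 30% as sizes of a relative change in FMD, not as fractions of patients, so a binomial variance would have no meaning for them.

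This is the only power statement in the protocol, and endothelial function is among the primary endpoints in the synopsis. If the 90% is taken at face value, a non-significant FMD change could be read as a well-powered negative result when the actual power is unknown.

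**Working it through.** **Inputs from section 6.1.3:** 10% (null), 30% (alternative), two-sided alpha 0.05, power 0.90, n = 40 evaluable, relevant difference 2 FMD points. Normal quantiles: 1.96 and 1.2816. The SD of change is not stated, so every SD below is an assumption. The step from 40 to 46 for dropout is not at issue here.

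**Step 1. Reproducing 40 by reading 10% and 30% as proportions (one sample, p0 = 0.10, p1 = 0.30).**

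- Arcsine: n = [(1.96 + 1.2816) / (2(arcsin√0.30 − arcsin√0.10))]² = 39.5, rounds up to 40.
- Score, uncorrected: n = [1.96√(0.10×0.90) + 1.2816√(0.30×0.70)]² / 0.20² = 34.5, rounds up to 35.
- Score with continuity correction: n' = (n/4)[1 + √(1 + 2/(0.20n))]² with n = 34.53 gives 39.4, rounds up to 40.
- Exact binomial, upper tail at most 0.025: power is 88.9% at n = 40 and 90.6% at n = 41, so 41 are needed.
- Null variance only: 23.6, rounds up to 24. Alternative variance only: 55.2, rounds up to 56.
- Two-sample comparison of proportions: 82 per group.

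Two standard one-sample formulas give 40 from the listed inputs with nothing added. The others do not.

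**Step 2. What 40 patients give for a mean within-patient change.** For a two-sided paired t-test, power follows from the noncentral t distribution with 39 degrees of freedom and noncentrality (change/SD)×√40. The normal approximation for the detectable standardised change at 90% power is (1.96 + 1.2816)/√40 = 0.513; the noncentral t gives 0.526.

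For a 2-point change tested against zero, the SD may therefore be at most 2/0.526 = 3.8 points. At other assumed SDs:

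| Assumed SD of change (FMD points) | Power at n = 40 | n for 90% power |
|---|---|---|
| 3 | 98% | 26 |
| 3.5 | 94% | 35 |
| 3.8 | 90% | 40 |
| 4 | 87% | 44 |
| 4.5 | 78% | 56 |
| 5 | 69% | 68 |
| 6 | 54% | 97 |

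**Step 3. The same on the relative scale.** With 30% tested against a null of 10%, the distance is 20 percentage points, and the SD may be at most 20/0.526 = 38 percentage points. Power is 98% at SD 30, 87% at 40, 69% at 50 and 54% at 60.

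**Step 4. The two scales are not interchangeable.** If 2 points is 20% to 30% of baseline, baseline FMD lies between 2/0.30 = 6.7 and 2/0.20 = 10. The 30%-versus-10% distance is then between 0.20×6.7 = 1.3 and 0.20×10 = 2.0 points. The tolerable SD therefore also depends on which scale and which null are meant.

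No SD in either range can be taken from the protocol, so no single corrected n follows.

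**The case against.** The strongest reply is that nothing stated has been shown to be false. A two-sided paired t-test gives n = 40 with 90.1% power for the protocol's own 2-point difference if the SD of change is 3.8 points, so 40 is compatible with a proper calculation whose SD was simply not reported. The section says it rests on previous data, which are not shown. The match with a proportion formula appears only under some variants: the uncorrected score gives 35 and the exact test 41. A missing SD might also be seen as a reporting gap in a descriptive single-arm study, and nothing in the protocol says that a non-significant FMD result will be read as evidence of no effect.

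Much of this stands. A reader might infer that the sponsor used the wrong formula, that 40 cannot come from any test of FMD change, or that the study is underpowered. The document supports none of these. The match is suggestive, not proof; 40 can be reached by a paired test; and the power could lie above or below 90%.

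What does not stand is that this is only a detail for a later document. The protocol itself carries out the calculation and presents 40 and 90% as its result. A statistical analysis plan could document an SD, but the 10%-versus-30% reasoning printed in 6.1.3 would still not lead to that n for a mean change.

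**Conclusion.** The point holds in this form: the inputs in 6.1.3 do not determine a sample size for a mean within-patient change in FMD, so the 90% power is not supported by the protocol. The 40 coincides with a one-sample 10%-versus-30% proportion calculation, which fits neither the continuous measure in 6.2.2 nor the analysis in section 8.

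Over assumed SDs of change from 3 to 6 points, power for a 2-point change runs from 98% down to 54%, and it reaches 90% only at about 3.8 points or less. These figures assume 40 evaluable patients, one paired comparison of two time points against zero, and a two-sided 0.05 level. A repeated measures analysis over many visits would also need the number of time points and the correlation between them, which 6.1.3 does not give either. The conclusion is that the power is unverified, not that it is shown to be low.

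**What to change.** Keep 40 evaluable patients and replace the power statement in section 6.1.3:

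- Remove the 10%-versus-30% formulation as the basis of n.
- Name the test, and state that 40 patients give 90% power (paired, two-sided 0.05) for a mean within-patient FMD change of 0.53 SD of the change.
- State the assumed SD of the change in FMD points, with its source.
- Give the resulting power for the 2-point difference over a range of SDs, for example 3 to 6 points.

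The cost is the rewording of one paragraph, with no extra patients, visits or measurements. The downside is that the power, once stated openly, may be less favourable than 90%.

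### Section 6.1.3: with 15% dropout, 46 enrolled patients leave about 39 evaluable, just under the 40 stated as required (minor arithmetic error)

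*Protocol*

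**What the plan says.** The only sample size statement in the protocol is section 6.1.3. It gives three linked figures.

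- Required number: "a sample of 40 patients is required for 90% power of detecting these differences", at an alpha of 0.05 and with the remark that "all tests are 2-sided".
- Loss and enrolment: "A dropout rate of 15% is assumed. A total number of 46 patients is thus calculated to be enrolled".

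The wording of the last sentence presents 46 as the result of applying the dropout rate to 40. The inflation formula is not printed. The protocol has no rule for replacing patients who drop out and gives no second enrolment target.

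**The concern.** A dropout rate is ordinarily a share of the patients enrolled. To end with 40 evaluable patients, the required number is therefore divided by the fraction retained. Multiplying it by one plus the dropout rate always gives too few, because the loss applies to the inflated number and not to the original one. The figure 46 looks like the result of that multiplication.

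What is at stake is the consistency of the paragraph. Taken together, 46 enrolled, 15% lost and 40 evaluable do not agree, and a report that quotes the sample size justification would carry the mismatch forward.

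**Working it through.** **Inputs, all from section 6.1.3:** required evaluable number n = 40; dropout rate d = 0.15; stated enrolment N = 46; two-sided alpha 0.05; power 90%. The 40 is taken as given. It cannot be recomputed, because no standard deviation of FMD or of its change is stated.

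**1. Reproducing the stated figure.** n × (1 + d) = 40 × 1.15 = 46.0, an exact match.

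**2. Enrolment that matches 15% and 40.** n / (1 − d) = 40 / 0.85 = 47.06, rounded up to 48. The unrounded value cannot round to 46.

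**3. Expected evaluable patients, N × 0.85.**

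| Enrolled | Expected evaluable |
|---|---|
| 46 | 39.1 |
| 47 | 39.95 |
| 48 | 40.8 |

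The expected shortfall at 46 is 40 − 39.1 = 0.9 of a patient.

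**4. Dropout that 46 can absorb.** (46 − 40) / 46 = 6/46 = 13.0%. In whole patients, six losses leave 40, and seven losses (7/46 = 15.2%) leave 39.

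**5. Effect on power, under an assumption.** The protocol names no test for this calculation. Assume a one-sample or paired two-sided comparison in which 40 patients give exactly 90% power, and solve for the standardised effect.

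- t-test: effect 0.526, power at 39 patients 89.2%.
- Normal approximation: effect (1.960 + 1.282)/√40 = 0.513, power at 39 patients 89.3%.

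If 40 is instead the smallest whole number that reaches 90%, power at 40 may lie a little above 90%. Under the t-test, power at 39 then lies between 89.2% and just under 90%.

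**6. Chance of reaching 40, under a further assumption.** If each patient drops out independently with probability 0.15, the probability of at least 40 evaluable patients is about 45% with 46 enrolled, 59% with 47 and 71% with 48.

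**The case against.** Several points can be made for leaving the paragraph alone.

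- *The gap is about one patient.* This stands. With 47 enrolled the expectation is 39.95, so the second patient in 48 comes only from rounding 47.06 up. The 15% is also a planning assumption and not a forecast to the decimal.
- *The 15% could be meant as a share of the 40 and not of those enrolled.* That reading does reproduce 46, but the text does not say so and it is not the usual meaning of a dropout rate.
- *Patients who leave may still contribute data.* Section 5.4.2 keeps following everyone who has not withdrawn consent, and section 8 plans linear mixed models. Some dropouts may therefore supply FMD measurements. This softens the practical effect but does not change the calculation in section 6.1.3, which still allows for a 15% loss from the number enrolled.
- *The cause is not documented.* This also stands. The match with 40 × 1.15 is exact, but the protocol does not show the step, so one can say only that 46 is consistent with it.

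A reader might go further and infer that the study is underpowered, or that its power falls to a known 89%. The documents support neither. The loss is under one percentage point on the assumptions shown, and the 89% rests on a test and an effect size that the protocol does not give. The null hypothesis in section 6.1.3 is also framed as a relative difference below 10% ("CFZ/Dex therapy is associated with <10% relative difference in FMD") and not as zero, so the test behind the 40 is not certain.

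**Conclusion.** The point holds as a minor arithmetic error. On the protocol's own figures, 46 enrolled patients with 15% dropout give 39.1 expected evaluable patients against the 40 required, and nothing elsewhere in the protocol makes up the difference. That result needs only the ordinary meaning of a dropout rate.

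The size is 0.9 of an evaluable patient, or two enrolled patients after rounding up, and less than one percentage point of power if 40 gives 90% in a one-sample or paired two-sided t-test. No endpoint, analysis or conclusion depends on it. Whether 40 is itself the right number is a separate matter that cannot be checked from the document.

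**What to change.** Change one sentence in section 6.1.3, in one of these ways.

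1. Keep 46 and state that it allows for about 13% dropout (6/46).
2. Keep 46 and 15%, and state that about 39 evaluable patients are then expected, slightly below the required 40. If a power figure for 39 is added (about 89%), label it as assuming that 40 gives exactly 90% power in a one-sample or paired two-sided t-test.
3. If both 15% and 40 are to be kept, state an enrolment of 48 (40/0.85 = 47.06, rounded up).

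The first two cost only the edit and need no further patients. The third adds two patients at the single site.

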6.1.4 History record

A detailed history will be obtained from every subject and all possible risk factors that could be associated with an increased risk of cardiac and vascular adverse events such as history of hypertension, coronary artery disease, arrhythmias, diabetes mellitus, dyslipidemia, smoking, renal disease. All medication that patients are receiving at the beginning of the study will also be recorded. Thorough clinical examination will also be performed along with ECG and cardiac echocardiography to ensure that every patient has an ejection fraction \geq 40% thus being eligible for enrollment. Data will be captured in a specifically designed CRF.

6.2 Functional and structural assessment of the vasculature

6.2.1 Assessment of arterial stiffness

Arterial stiffness in the aorta by measurement of pulse wave velocity (PWV)

Carotid-femoral pulse wave velocity (c-f PWV) is an established index of aortic stiffness and an independent predictor of worse cardiovascular prognosis(21, 22). It is considered as the gold standard for assessing aortic stiffness non-invasively and is calculated from measurements of pulse transit time and the distance travelled between 2 recording sites with a validated non-invasive device (Complior, Artech Medical, France). Two different pulse waves are obtained at the same time transcutaneously with the patient in a supine position at 2 sites, at the right common carotid artery and the right femoral artery (i.e. 'carotid-femoral' PWV) by using pressure-sensitive transducers. The distance traveled by the pulse wave is measured over the body surface and calculated by subtracting the carotid (sternal notch from the carotid)-femoral distance as distance/time (m/s)(23). Distance should be measured precisely because small inaccuracies may influence the absolute value of PWV (24). Moreover, the femoral pressure waveform may be difficult to record accurately in patients with metabolic syndrome, obesity, diabetes, and peripheral artery disease. The velocity of the pulse wave as it traverses the arterial tree is critically dependent on characteristics of the conduit artery wall, with pulse travelling at a higher velocity through stiffer arterial vessels (25). The principal determinants of PWV are described by the Moens-Korteweg equation that was derived in the 1920s, and relates the velocity of pulse wave travel in a vessel to the distensibility of that vessel where co is the wave speed, E is Young's modulus in the circumferential direction, h is the wall thickness, R is the vessel radius and p is the density of fluid. In a given blood vessel filled with blood of fixed density, PWV is proportional to the square root of the Young's modulus of elasticity of the vessel. In other words, the stiffer the vessel, the faster the PWV.

Central blood pressures and reflected waves in the aorta

Non-invasive estimation of aortic pressure waveforms and reflected waves by pulse wave analysis (PWA) will be performed in the Angiology laboratory by the SphygmoCor System (AtCor Medical Pty Ltd, Sydney, Australia). The radial artery is gently and steadily compressed against the underlying bone, thus flattening it and equalizing circumferential pressures, allowing radial pressure waves to be recorded by a high fidelity micromanometer placed on the tip of a hand – held tonometer the size of a pen (Millar). Optimal recording is obtained if the wrist is bent outward and supported by using a small cushion or the operator's hand. The following indices are measured: a. augmentation index (AI, percentage) normalized for the heart rate of 75 bpm, expressed as a percentage of the aortic pulse pressure, b. central systolic and diastolic pressures (cBP), c. time to the beginning of the reflected wave (in milliseconds) and d. blood pressure amplification calculated as the ratio of peripheral pulse pressure: central pulse pressure. Central pressure waves are

derived by use of transfer functions and augmentation index (Alx) is used as a measure of reflected waves. As described before in the case of stiff arteries, PWV rises and the reflected wave arrives back at the central arteries earlier, adding to the forward wave and augmenting the systolic pressure. This phenomenon is quantified through the augmentation index—defined as the difference between the first and second systolic peaks expressed as a percentage of the pulse pressure (difference between systolic and diastolic blood pressure)(26).

6.2.2 Endothelial function by ultrasound measurement of endothelium-dependent flowmediated dilatation (FMD)

Endothelial function will be assessed by Flow Mediated Dilatation (FMD) using a 7-14 MHz probe (Vivid 7 Pro, GE, USA) as previously described (27). After a 15-min rest in supine position in a quiet, climate-controlled room (22 ±1°C), the internal diameter of the brachial artery of the subject is assessed. Upper arm occlusion by supra-systolic level (50 mmHg above systolic blood pressure) is applied via a cuff fitted 8-cm distal to the brachial artery (in the antecubital fossa) and near the wrist for 5 min. The cuff is released following the 5-min inclusion to induce reactive hyperemia. This increase in shear stress results in endotheliumdependent flow-mediated dilation (FMD). Data are recorded 2 minutes before and immediately after cuff release to measure peak blood flow and brachial artery diameter for 2 min after cuff deflation. ECG-gated frames of brachial artery diameter are continuously recorded and brachial artery diameter is measured offline using dedicated border detection software (Brachial Analyzer for Research, MIA IIc, USA). Flow-mediated dilatation is induced in response to reactive hyperemia and is expressed as the percentage change of internal diameter of the brachial artery from baseline. Flow-mediated dilatation has been previously shown to be nitric oxide dependent in humans and it is considered as a marker of endothelial function (28-29). Ultrasound analysis will be performed in each case manually by a qualified independent observer blinded to the clinical history of the subjects.

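### Section 6.2.2 masks the FMD reader to clinical history but specifies no masking to visit, date or pre/post-dose status, which is the contrast the study tests

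*Protocol*

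**What the plan says.** Protocol section 6.2.2 describes how FMD is obtained and read. ECG-gated frames are recorded before and after cuff release, and "brachial artery diameter is measured offline using dedicated border detection software". FMD is the percentage change in that diameter from its pre-cuff value. The section then gives the only reader-blinding statement in the protocol: "Ultrasound analysis will be performed in each case manually by a qualified independent observer blinded to the clinical history of the subjects". It says nothing about visit, scan date, pre/post-dose status or reading order.

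Section 6.1.3 bases the sample size on FMD: "at least 2% absolute difference in Flow mediated dilatation (FMD) (corresponding to 20-30% relative difference) is considered significant and clinically relevant". The null is that "CFZ/Dex therapy is associated with <10% relative difference in FMD", the alternative is that a "30% difference is considered as significant" or more, and "a sample of 40 patients is required for 90% power of detecting these differences" ("all tests are 2-sided").

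The synopsis lists endothelial function among the primary endpoints, as change before, during and after treatment. Sections 6.2.4 and 7 schedule measurements before and 2 hours after dosing over several visits. Section 8 plans repeated measures ANOVA over time. There is no control group.

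**The concern.** A mask protects a comparison when it hides the factor being compared. Here that factor is the time of the scan: baseline against later, pre-dose against post-dose. The separation of the dexamethasone effect from the carfilzomib effect (section 6.1.2) is also defined by time point alone. Masking to clinical history protects comparisons between patients with different risk factors, and so helps the confounder-adjusted models. It does not cover the within-patient contrast, because every patient has myeloma and receives the same drugs.

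If the reader can see the time point and reads even slightly differently by it, the result has the form of a treatment effect, and there is no control arm from which to subtract it. Section 4.1 B also relates the degree of vascular deterioration to proteasome activity. Both would move with dosing, so a reading shift tied to dose timing could enter that association too.

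**Working it through.** **1. The protocol's own figure.** The 40 patients can be neither confirmed nor refuted, because no SD of FMD change is given. The implied SD can be backed out for a paired mean, two-sided 0.05, 90% power:

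- Standardized change = (1.960 + 1.282)/√40 = 0.513.
- Two points equal to 20-30% relative implies a baseline FMD of 2/0.30 = 6.7% to 2/0.20 = 10%.
- For a 2-point difference, SD = 2/0.513 = 3.9 points.
- For 30% against the 10% null, the difference is 20% of baseline: 1.33 points at 6.7% (SD = 1.33/0.513 = 2.6) or 2 points at 10% (SD = 3.9).

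The SD of 2.6 to 3.9 points used below is therefore implied, not stated.

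**2. A uniform reading shift on one scan.** Assume a 4.00 mm artery and a true FMD of 8%, so the peak is 4.32 mm. Add 0.02 mm to every frame:

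- (4.34 − 4.02)/4.02 = 7.96%, a change of 0.04 points, or 0.04/2 = 2% of the relevant difference.
- In general the FMD is multiplied by 4.00/4.02 = 0.995, so over baselines of 6.7-10% the change is about 0.03 to 0.05 points.

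A uniform shift nearly cancels, because each scan supplies both numerator and denominator.

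**3. A differential shift.** Add the shift only to the post-deflation frames of post-dose scans, leaving the pre-cuff frames untouched. The bias is 100 × shift/diameter:

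| Shift (assumed) | Bias in a 4 mm artery | Share of 2 points |
|---|---|---|
| 0.01 mm | 0.25 points | 12.5% |
| 0.02 mm | 0.5 points | 25% |
| 0.04 mm | 1.0 point | 50% |

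For example, (4.34 − 4.00)/4.00 = 8.5% against 8.0%.

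**4. Effect on the error rate, taking such a bias b as given.** With SE = SD/√40, the two-sided type I error of a z test on one pre/post contrast is 1 − Φ(1.96 − b/SE) + Φ(−1.96 − b/SE).

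| b (points) | SD 2.6 (SE 0.411) | SD 3.9 (SE 0.617) |
|---|---|---|
| 0.25 | 0.093 | 0.069 |
| 0.5 | 0.229 | 0.128 |
| 1.0 | 0.682 | 0.368 |

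The diameter, the shifts and the SD range are assumptions. The z test is a simplification of the planned ANOVA. The tables show how sensitive the comparison is, not that a bias exists.

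**The case against.** The strongest reply is that this is silence, not an adverse statement. The protocol nowhere says that the reader sees visit or dose labels, and coding and reading order may sit in an imaging manual that is not at hand. That stands: a reader might infer that the observer is unmasked to time point, and the text does not say so. But section 6.2.2 does define the reader's mask and names only clinical history, so a reader who sees the labels would still comply with it.

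Second, the independent observer, ECG gating and border detection software limit discretion. This stands in part. The same section calls the analysis manual, and independence does not hide a scan date.

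Third, one might infer that nothing in the design could expose a reader effect. That is too strong. Ambulatory blood pressure, device-based pulse wave velocity, tonometric wave analysis and laboratory proteasome activity do not depend on this reader, and an FMD change made only by the reader would not be expected to track them. They are imperfect checks, but they exist.

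Fourth, one might assume a reader who expects deterioration. Section 1 presents conflicting evidence, with both harm and benefit to endothelial function, and the tests are two-sided. Section 4.1 B does speak of deterioration, but the protocol fixes no settled direction.

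**Conclusion.** The point holds as a gap in what section 6.2.2 specifies. The mask it states does not cover the time contrast that FMD is used to test, in a single-arm design whose sample size rests on FMD.

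The size of any bias is unknown. A reader might infer that any 0.02 mm shift on post-dose scans costs 0.5 FMD points. It does not: a uniform shift changes FMD by about 0.04 points. The 0.5-point figure, a quarter of the relevant difference, requires a shift confined to the post-deflation frames of post-dose scans in an assumed 4 mm artery. If a bias of that size did occur, type I error for one contrast would be about 0.13 to 0.23 under the implied SD. No sample size or power figure changes.

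Extending the point to intima-media thickness and plaque echogenicity is weakly supported. Section 6.2.4 limits the carotid and femoral scans to baseline, with at most a cycle 6 repeat, and section 6.2.3 describes the echogenicity software as automated.

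**What to change.** In section 6.2.2, state that stored FMD recordings are coded and read offline in random order within patient, with the reader masked to visit, date, pre/post-dose status and clinical history. If an imaging manual already requires this, a cross-reference is enough. The same rule may be applied to the offline strain readings at baseline and 6 months (section 6.3).

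The cost is coding the files and some delay, because a patient's recordings must be collected before they can be shuffled. No extra reader, scan or patient is needed. Recordings already read without masking would have to be re-read to gain the benefit.
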